7.0 STUDY PROCEDURES

7.1 Schedule of Study Procedures

Study evaluations are summarized in Table 4 below and described in Sections 7.2 through 7.2.7.

The Principal Investigator is responsible for ensuring that all staff involved in the study are familiar with the content of this section.

Table 4. Schedule of Study Evaluations

Day	Pretreatment ¹	Cycle 1					Cycle 2 and Subsequent Cycles					EoT	FU ¹²		
		1	2	3	4	5	19	1	2	3	4				
Eligibility Criteria	X														
Registration / Informed Consent	X														
Medical History	X	X*													
Tumor Assessment	X													X ⁶	X
Physical Exam / ECOG	X	X													X
Vital Signs	X	X	X	X	X										
Hematology	X	X*				X**									
Coagulation	X	X*													
Blood Chemistry	X	X*				X**									
Creatinine Clearance	X														
CA-125	X	X*												X*	X
Urinalysis	X	X*												X*	
Serum Pregnancy Test (Females of Childbearing Potential)	X														
LVEF ²	X													X ²	
ECG in selected patients, at sites given Mortara 12-lead recorder	X	X												X ^{3,4}	X
ECG in selected patients, at sites given Holter ⁴	12-lead	24h Holter													
ECG, non-selected patients	X														
Tumor Biopsy ⁵	X					X									
Exploratory Biomarkers – Whole Blood	X ⁷														
Exploratory Biomarkers – Plasma		X ⁸												X ⁸	X

**Aprea Therapeutics AB PiSARRO-R: p53 Suppressor Activation in Platinum-Resistant High Grade
Protocol No. APR-486 Serous Ovarian Cancer, a Phase II Study of Systemic Pegylated Liposomal
Doxorubicin Chemotherapy With APR-246**

Day	Pretreatment ¹		Cycle 1					Cycle 2 and Subsequent Cycles					EoT	FU ¹²	
	1	2	3	4	5	19	1	2	3	4	25-28				
Administer APR-246	X	X	X	X				X	X	X	X				
Administer PLD				X								X			
Pharmacokinetics ¹⁰	X	X ⁴		X	X ⁴			X				X			
New anticancer treatment ¹¹															
Adverse Events and Concomitant Medication ¹³								X							X

Examinations marked * need not be repeated if already performed within +/-3 days prior to Day 1.

Examinations marked ** may be performed within +/-2 days.

1. Pretreatment evaluations to be performed within 28 days prior to Day 1.
2. LVEF assessed by echocardiography. At pretreatment and within 7 days prior to the start of Cycle 3 and Cycle 6 and every 3rd cycle thereafter. In addition, evaluation of LVEF is mandatory before each additional administration of PLD that exceeds a lifetime cumulative anthracycline dose of 450 mg/m².
3. Optional rhythm strip performed using limb leads of 12-lead ECG machine, after the end of APR-246 infusion.
4. These assessments will be discontinued once sufficient evaluable data has been collected.
5. An optional tumor biopsy to be performed prior to Day 1 APR-246 infusion and on Cycle 1 Day 3, as per laboratory manual.
6. CT scan/MRI at the end of Cycle 2 (within 4 days prior to the start of Cycle 3), and at the end of Cycle 4 (within 4 days prior to the start of Cycle 5) and every two cycles thereafter. In patients who have discontinued therapy without progression, scans will be performed every 8 weeks until progression has occurred.
7. Blood sample taken within 72 hours of pretreatment biopsy.
8. Blood samples taken before infusion of APR-246 in Cycles 1, 2 and 6.
9. Blood samples should be taken at each follow-up visit before progression and at progression, as per laboratory manual.
10. Pharmacokinetics: please refer to Section 8.4.
11. New anticancer treatment to be collected in eCRF during follow up.
12. Follow-up visits should be performed at least every 8 weeks.
13. AEs will be collected throughout the study, from informed consent until 30 days after the last administration of study treatment.

7.2 Detailed Study Evaluations

The following sections provide details of the study evaluations to be conducted pretreatment, during study and in follow-up. Please refer to Table 4 for a complete schedule of assessments required.

7.2.1 Registration/Informed Consent Form

Prior to performing any procedures or assessments, the nature of the study and the potential risks associated with the trial will be explained to all subject candidates and written informed consent will be obtained. Subjects who choose to participate will have to consent to the biobanking program and will be asked to sign the mandatory section in the main study consent form related to biobank samples. Evaluations obtained as part of routine medical care and performed during the screening period may be used in place of the study-specific evaluations. Subjects will acknowledge and agree to the possible use of this information for the study by giving informed consent.

7.2.2 Pretreatment

All pretreatment evaluations are to be performed within 28 days prior to Day 1 unless otherwise noted. Please see Table 4 for treatment windows for individual evaluations.

- **Eligibility criteria:** Including archived tumor sample review for positive IHC staining for p53.
- **Registration.**
- **Medical history.** Including documentation of all previous therapies for ovarian cancer.
- **Tumor assessment:** CT scan/MRI to be performed within 4 weeks prior to Day 1.
- **Physical examination:** Height, weight, body surface area and description of external signs of cancer. To be performed by an authorized investigator or nurse.
- **ECOG performance status.**
- **Vital signs:** Heart rate, blood pressure, respiratory rate and temperature.
- **Hematology:** Hemoglobin, hematocrit, mean corpuscular volume, platelet count, white blood cell count (WBC) and WBC differentials.
- **Coagulation:** INR and activated partial thromboplastin time (APTT). If patient is receiving warfarin, assessments should be done weekly.
- **Blood chemistry:** Sodium, potassium, calcium, magnesium, chloride, glucose, creatinine, total bilirubin, AST, ALT, urea, total protein, albumin and lactic dehydrogenase (LDH), direct bilirubin and uric acid.
- **Creatinine clearance:** Calculated as per hospital practice.
- **CA-125.**
- **Urinalysis:** Dipstick for protein, glucose, bilirubin and blood (perform microscopy if more than one positive dipstick test).
- **Serum pregnancy test:** For patients with reproductive potential.
- **LVEF:** Assessed by echocardiography.
- **ECG:** Standard 12-lead ECG, taken in triplicate (use Mortara ELI 150RX 12 lead ECG

Recorder if provided).

- **Tumor biopsy (optional):** To be performed prior to Day 1 APR-246 infusion, as per laboratory manual.
- **Exploratory biomarkers:** Whole blood sample taken within 72 hours of pretreatment biopsy. The sample will be collected in order to sequence target genes of germline DNA. Archive pathology samples and blood samples to be sent for centralized analysis after registration. Refer to Laboratory Manual for detailed instructions.
- **AEs:** From the date the Informed Consent form is signed.
- **Concomitant medication.**

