5.0 SELECTION AND WITHDRAWAL OF PATIENTS

5.1 Inclusion Criteria

To be eligible to participate in this study, patients must meet all of the following inclusion criteria:

1. Archived sections from the original formalin fixed paraffin embedded sample reviewed by a gynecological pathologist confirming HGSOE, high grade serous peritoneal cancer or primary fallopian tube cancer and positive immunohistochemistry staining for p53 assessed according to the local methodology (as detailed in the laboratory manual). Cases that do not show p53 staining will not be included.
2. Disease progression between 4 weeks and 6 months after the last platinum-based treatment was administered.
3. At least a single (RECIST 1.1) measurable lesion.
4. Adequate organ function prior to registration:
 - a) Bone marrow reserve
 - Absolute neutrophil count (ANC) $\geq 1.5 \times 10^9/L$
 - Platelets $\geq 100 \times 10^9/L$
 - Hemoglobin ≥ 9 g/dL
 - b) Hepatic
 - Total bilirubin level $< 1.5 \times$ upper limit of normal (ULN) without hepatic metastasis, and $< 4 \times$ ULN with hepatic metastasis
 - Alanine aminotransferase (ALT) and aspartate aminotransferase (AST) $< 2.5 \times$ ULN without hepatic metastasis, and $< 4 \times$ ULN with hepatic metastasis
 - c) Renal
 - Calculated creatinine clearance > 30 mL/min calculated per local practice
 - d) Electrolytes
 - Potassium within institutional normal ranges.
5. Toxicities from previous cancer therapies (excluding alopecia) must have recovered to grade 1 (defined by National Cancer Institute [NCI] Common Terminology Criteria for Adverse Events [CTCAE] version 4.0). Chronic stable grade 2 peripheral neuropathy secondary to neurotoxicity from prior therapies may be considered on a case by case basis by the Principal Investigator.
6. If of childbearing potential, negative pretreatment serum pregnancy test.
7. If of childbearing potential, willing to use an effective form of contraception (see below)

during chemotherapy treatment and for at least 6 months thereafter. Such methods include the following (if using hormonal contraception, this method must be supplemented with a barrier method, preferably male condom):

- combined (estrogen and progestogen containing) hormonal contraception associated with inhibition of ovulation:
 - oral
 - intravaginal
 - transdermal
 - progestogen-only hormonal contraception associated with inhibition of ovulation:
 - oral
 - injectable
 - implantable
 - intrauterine device (IUD)

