7.2.4 All Cycles, Days 1-28

Day 1 examinations marked * do not need to be repeated if already performed within +/-3 days prior to Day 1. Examinations marked ** may be performed within +/- 2 days.

- **Medical history:** Day 1*
- **Physical examination:** Day 1. Height, weight, body surface area and description of external signs of cancer. To be performed by an authorized investigator or nurse.
- **ECOG performance status:** Day 1.
- **Vital signs:** Days 1, 2, 3 and 4. Only on Cycle 1 perform also on day 19** . Heart rate, blood pressure, respiratory rate and temperature.
- **Hematology:** Cycle 1 performed on Days 1*, 4** and 19** (repeat to follow up on AEs as appropriate). Subsequent cycles perform only on Day 1* . Hemoglobin, hematocrit, mean corpuscular volume, platelet count, WBC and WBC differentials.
- **Coagulation:** Day 1* INR and APTT. If patient is receiving warfarin, assessments should be done weekly.
- **Blood chemistry:** Cycle 1 perform on Days 1* and 4** (repeat to follow up on AEs as appropriate). Subsequent cycles perform only on Day 1* . Sodium, potassium, calcium, magnesium, chloride, glucose, creatinine, total bilirubin, AST, ALT, urea, total protein, albumin and LDH, direct bilirubin and uric acid.
- **CA-125:** Day 1* .
- **Urinalysis:** Day 1* . Dipstick for protein, glucose, bilirubin and blood (perform microscopy if more than one positive dipstick test).
- **LVEF:** Assessed by echocardiography within 7 days prior to Cycle 3 and Cycle 6 and every 3rd cycle thereafter. LVEF is mandatory before each additional administration of PLD that exceeds a lifetime cumulative anthracycline dose of 450 mg/m².
- **Tumor biopsy:** Cycle 1 only (optional). Tumor biopsy performed optimally at the end of APR-246 infusion on Day 3 of the first cycle, however a biopsy obtained at the end of the

APR-246 infusion on Day 2 is acceptable. Refer to Laboratory Manual for detailed instructions.

- **Exploratory biomarkers:** Blood samples taken before infusion of APR-246 on Day 1 of Cycles 1, 2 and 6. The plasma samples will be collected in order to analyze circulating tumor DNA. Refer to Laboratory Manual for detailed instructions.
- **APR-246 administration:** Days 1, 2, 3 and 4.
- **PLD chemotherapy administration:** Day 4.
- **AEs:** Even though premedicated, patients should be closely monitored for hypersensitivity reactions, especially during the first cycle.
- **Concomitant medications.**

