A “reasonable possibility” could be considered to exist for an AE where one or more of these factors exist. In contrast, there would not be a “reasonable possibility” of causality if none of the above criteria apply or where there is evidence of exposure and a reasonable time course but any dechallenge (if performed) is negative or ambiguous or there is another more likely cause of the AE.

In difficult cases, other factors could be considered such as:

- Is this a recognized feature of overdose of the IMP?
- Is there a known mechanism?

Ambiguous cases should be considered as being a “reasonable possibility” of a causal relationship unless further evidence becomes available to refute this. Causal relationship in cases where the disease under study has deteriorated due to lack of effect should be classified as no reasonable possibility.

Appendix V: Actions Required in Cases of Increases in Liver Biochemistry and Evaluation of Hy's Law

1. Introduction

This Appendix describes the process to be followed in order to identify and appropriately report cases of Hy's Law. It is not intended to be a comprehensive guide to the management of elevated liver biochemistries.

During the course of the study the Investigator will remain vigilant for increases in liver biochemistry. The investigator is responsible for determining whether a patient meets potential Hy's Law (PHL) criteria at any point during the study.

The Investigator participates, together with Aprea Therapeutics AB's representatives, in review and assessment of cases meeting PHL criteria to agree whether Hy's Law (HL) criteria are met. HL criteria are met if there is no alternative explanation for the elevations in liver biochemistry other than drug-induced liver injury (DILI) caused by the IMP.

The Investigator is responsible for recording data pertaining to PHL/HL cases and for reporting AEs and SAEs according to the outcome of the review and assessment in line with standard safety reporting processes.

2. Definitions

Potential Hy's Law (PHL)

AST or ALT ≥ 3 x ULN together with total bilirubin (TBL) ≥ 2 x ULN at any point during the study following the start of study medication irrespective of an increase in ALP.

Hy's Law (HL)

AST or ALT ≥ 3 x ULN together with TBL ≥ 2 x ULN, where no other reason, other than the IMP, can be found to explain the combination of increases, e.g., elevated ALP indicating cholestasis, viral hepatitis, another drug.

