 - The ‘Medically Important’ serious criterion should be used if no other serious criteria apply
 - As there is no alternative explanation for the HL case, a causality assessment of ‘related’ should be assigned.

If, there is an unavoidable delay, of over 3 weeks, in obtaining the information necessary to assess whether or not the case meets the criteria for HL, then it is assumed that there is no alternative explanation until such time as an informed decision can be made:

- Report an SAE (report term ‘Potential Hy’s Law’) applying serious criteria and causality assessment as per above
- Continue follow-up and review according to agreed plan. Once the necessary supplementary information is obtained, repeat the review and assessment to determine whether HL criteria are met. Update the SAE report according to the outcome of the review.

6. Actions Required When Potential Hy’s Law Criteria are Met Before and After Starting Study Treatment

This section is applicable to patients who meet PHL criteria on study treatment having previously met PHL criteria at a study visit prior to starting study treatment.

At the first on study treatment occurrence of PHL criteria being met the Investigator will:

- Determine if there has been a significant change in the patient’s condition[#] compared with the last visit where PHL criteria were met[#]
 - If there is no significant change no action is required
 - If there is a significant change, notify the Theradex representative then follow the subsequent process described in Section 4.2 of this Appendix.

A ‘significant’ change in the patient’s condition refers to a clinically relevant change in any of the individual liver biochemistry parameters (ALT, AST or total bilirubin) in isolation or in combination, or a clinically relevant change in associated symptoms. The determination of whether there has been a significant change will be at the discretion of the Investigator; this may be in consultation with the Medical Monitor if there is any uncertainty.

7. Actions Required for Repeat Episodes of Potential Hy’s Law

This section is applicable when a patient meets PHL criteria on study treatment and has already met PHL criteria at a previous on study treatment visit.

The requirement to conduct follow-up, review and assessment of a repeat occurrence(s) of PHL is based on the nature of the alternative cause identified for the previous occurrence.

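### Appendix V names elevated ALP as a reason to rule out Hy's Law, but no baseline or same-sample ALP is scheduled

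*Combined protocol and SAP*

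**What the plan says.** Section 7.2.2 lists the pretreatment chemistry analytes one by one: "Sodium, potassium, calcium, magnesium, chloride, glucose, creatinine, total bilirubin, AST, ALT, urea, total protein, albumin and lactic dehydrogenase (LDH), direct bilirubin and uric acid". Section 7.2.4 repeats the list for the treatment cycles, and its liver-related part reads "creatinine, total bilirubin, AST, ALT, urea, total protein, albumin and LDH, direct bilirubin and uric acid". The schedule in Table 4 has only a row for blood chemistry and adds no analytes. The end-of-treatment visit in Section 7.2.5 lists no chemistry. Apart from the abbreviation list, ALP appears only in Appendix V.

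Appendix V works in two steps. A potential Hy's Law case needs AST or ALT of at least 3 x ULN together with total bilirubin of at least 2 x ULN, "at any point during the study following the start of study medication irrespective of an increase in ALP". A Hy's Law case has the same elevations, but "where no other reason, other than the IMP, can be found to explain the combination of increases, e.g., elevated ALP indicating cholestasis"; viral hepatitis and another drug are the other two examples given.

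When the potential criteria are met, Appendix V Section 4.2 calls for diagnostic investigations agreed with the Medical Monitor, without naming ALP. Section 5 then has the Investigator and Medical Monitor, with the sponsor and other experts, decide whether another explanation exists. If none is agreed, the case is reported as an SAE with causality set to related.

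**The concern.** The step that separates a potential case from a Hy's Law case relies, in its first example, on an analyte that the protocol does not schedule. A site that follows the protocol exactly will have AST, ALT, total bilirubin and direct bilirubin before treatment and at each chemistry draw, but no ALP at any of them. If ALP is first measured during the work-up and is raised, the reviewers cannot tell from scheduled data whether it was already raised before APR-246 or rose with the transaminases.

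At stake is the attribution of liver events to APR-246. Safety is a secondary objective of the Main Study and a primary objective of the Sub-Study. In patients with liver metastases, cholestasis from tumor is a natural competing explanation, and a pretreatment value is the most direct way to see whether a raised ALP is long-standing.

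**Working it through.** No figure in the plan has to be reproduced. The check sets the lists against the definitions and compares two sets of limits.

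**Step 1. Analytes used against analytes scheduled**

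| Analyte | Role in Appendix V | In 7.2.2 list | In 7.2.4 list |
|---|---|---|---|
| ALT | Potential Hy's Law | Yes | Yes |
| AST | Potential Hy's Law | Yes | Yes |
| Total bilirubin | Potential Hy's Law | Yes | Yes |
| ALP | First example of another explanation | No | No |

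Each list has 16 analytes. All three analytes needed for detection are present. ALP, the only routine chemistry analyte named in the exclusion step, is in 0 of 2 lists.

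**Step 2. How often the companion values are drawn**

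Chemistry is scheduled at pretreatment (1), on Days 1 and 4 of Cycle 1 (2), and on Day 1 of each later cycle. A patient treated for k cycles therefore has 1 + 2 + (k - 1) = k + 2 scheduled sets. One fewer applies if the pretreatment sample falls within 3 days of Day 1 and is not repeated. For ten cycles, the period over which within-cycle data are collected, that is 10 + 2 = 12 sets (or 11). The number of scheduled ALP values is 0.

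**Step 3. Can a patient enter at potential Hy's Law levels?**

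The entry limits are in Section 5.1, criterion 4b; the thresholds are in Appendix V Section 2.

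| | Entry limit, no hepatic metastasis | Entry limit, hepatic metastasis | Potential Hy's Law threshold |
|---|---|---|---|
| AST/ALT | < 2.5 x ULN | < 4 x ULN | >= 3 x ULN |
| Total bilirubin | < 1.5 x ULN | < 4 x ULN | >= 2 x ULN |

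- Without hepatic metastasis both limits lie below the thresholds (2.5 < 3 and 1.5 < 2), so an eligible patient cannot enter at those levels.
- With hepatic metastasis the ranges overlap: AST or ALT from 3 to just under 4 x ULN, with bilirubin from 2 to just under 4 x ULN. Such a patient is eligible and already at the thresholds. Appendix V foresees this, since its Section 6 deals with patients who met the criteria before treatment.

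**Step 4. What the work-up can and cannot recover**

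An ALP drawn after the trigger supplies a current value. It cannot supply a pretreatment one. Nor does the protocol ensure an ALP from the sample that showed the elevation.

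**The case against.** The case on the other side is substantial, and most of it stands.

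- **Hy's Law is not meant to be decided from scheduled data.** ALP is one of three examples ("e.g., elevated ALP indicating cholestasis, viral hepatitis, another drug"). Viral serology is not scheduled either. The decision rests on a triggered work-up and a joint review. A reader might infer that cases cannot be classified at all. The documents do not support that, because ALP can be drawn in the work-up.
- **Detection is complete without ALP.** The trigger uses only ALT, AST and bilirubin, so no potential case is missed for want of ALP.
- **Other evidence on cholestasis is scheduled.** Direct bilirubin is in both panels, and CT or MRI is done before treatment and every two cycles.
- **The 3-week default.** A reader might infer that missing ALP would push cases into the rule under which "then it is assumed that there is no alternative explanation until such time as an informed decision can be made". That rule covers only an unavoidable delay of over 3 weeks, and nothing suggests that an ALP result would take so long. The resulting SAE is termed Potential Hy's Law, is provisional, and is updated after re-review.
- **Patients abnormal at entry have their own path.** Appendix V Section 6 asks for action only on a significant change in ALT, AST, bilirubin or symptoms. This narrows the group for whom a baseline ALP is wanted, but those who do change go to the same work-up without one.
- **The listed panel is a minimum.** Section 7.2.1 lets routine-care results obtained during screening stand in for study evaluations, Section 7.2.4 allows repeat chemistry to follow up AEs, and the laboratory manual is not among the documents. Some patients may have ALP values. The protocol does not ensure it.

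None of these points supplies a pretreatment ALP by design.

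**Conclusion.** The point holds as a gap in scheduled data. Appendix V names elevated ALP as a reason to separate potential Hy's Law from Hy's Law, and the protocol schedules neither a baseline nor a same-sample ALP. It weakens attribution in the work-up. It does not affect detection of potential cases, the primary endpoint, power or type I error.

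The omission applies to all patients, about 50 if both parts enrol 25, but it has a consequence only for those who meet the potential criteria and in whom cholestasis is a plausible cause. The documents give no expected number of such patients, and it may be zero. A reader might wish to express the effect as a change in a Hy's Law rate. No such rate is an endpoint or a planned summary, so that would measure nothing the trial reports.

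The conclusion assumes that the itemised lists are the complete protocol panel and that the laboratory manual does not add ALP. If it does, the remaining task is to bring the protocol text into line.

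**What to change.** Add ALP to the blood chemistry lists in Sections 7.2.2 and 7.2.4, at the time points where AST, ALT and bilirubin are already drawn. In Appendix V Section 5, list ALP, with its pretreatment value, among the data reviewed for each potential case. The trigger thresholds and the definition of significant change in Appendix V Sections 6 and 7 can stay as they are.

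The cost is one extra analyte on existing samples, one eCRF field and a short protocol amendment, with no new visit or blood draw. The change will not settle every case: viral hepatitis and other drugs still need the unscheduled work-up. Patients enrolled before the change would lack the baseline value unless a routine-care result exists, so the review should record whether one was available.
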